## 3.2.1 Endpoints for secondary objectives

Endpoints for the secondary efficacy objectives are as follows (detailed definitions are given in Section 10.5.1.1):

- Proportion of patients with hematologic improvement in terms of erythroid response
- Overall survival
- Proportion of patients with hypothyroidism as assessed by annual TSH and free T4
- Proportion of patients with a worsening of glucose metabolism from baseline as assessed by annual oral glucose tolerance test (OGTT)
- Time to disease progression, i.e. either MDS progression defined as a transition into a higher MDS risk group based on IPSS scoring or to progression to AML as defined in Section 7.5.9.
- Time to first occurrence of serum ferritin > 2 times the baseline value at two consecutive assessments (at least two weeks apart)
- Time to at least a 10% increase from baseline in left ventricular end-diastolic internal dimension (LVIDD) at two consecutive assessments at least two weeks apart
- Time to at least a 10% increase from baseline in left ventricular internal systolic diameter (LVISD) at two consecutive assessments at least two weeks apart
- Frequency and rate of infections requiring intravenous antimicrobials (Fenaux 2009)

Endpoints for the other secondary safety objectives are as follows (detailed definitions are given in Section 10.5.2.2):

- Proportion of patients with significant renal dysfunction defined as serum creatinine  $\geq 2$  times ULN at two consecutive assessments (at least 7 days apart)
- Proportion of patients with newly occurring moderate (CTCAE Grade 3) or severe (CTCAE Grade 4) neutropenia or thrombocytopenia

- Proportion of patients with major gastrointestinal bleeding
- Time to study drug discontinuation due to an adverse event or laboratory abnormality
- Incidence of other adverse events and laboratory abnormalities

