Week 	-5 1	to -	Day 1	2	4	8	12	16	20	24	28	32	36	40	44	48	52	56 368	372				

- 15. Transfusions may be administered as necessary throughout the study and number and volume (ml) of PRBC and platelets administered are to be recorded in eCRF.
- 16. Required for Females of child bearing potential only.
- 17. A 2 hour fasting Glucose Tolerance test will be done at screening and annually (Weeks 52, 104, 156, 208, 260, 312, 364) and at study treatment discontinuation. Patients should fast for at least 5 hours prior to the test being drawn. Should a patient have a documented diagnosis of diabetes requiring treatment with medication, the Glucose Tolerance Test is not mandatory and is up to the Investigator's discretion. The Glucose Tolerance Test should be performed annually during the Evaluation Period.
- 18. Visit Windows: The following visit windows are permitted: ±3 days Weeks 2 & 4; ±7 days for every monthly visit (Weeks 8, 12, 16, 20 through EOT); ±2 weeks for Evaluation and Survival Follow-Up visits

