#### 7.5.5.5 **Pregnancy test**

All female patients capable of becoming pregnant will have a pregnancy test (serum β-HCG) at screening visit 1. When performed at screening, the results of the test must be available prior to initiating treatment with any study medication. Positive pregnancy tests will exclude a patient from participating in this trial.

Urine pregnancy testing will be performed locally at the End of Treatment visit and if menses are delayed for more than 7 days in a female patient capable of becoming pregnant. See Section 8.2 for procedures to report pregnancy.

Table 7-2 Laboratory evaluations

Evaluation	Sample collection	Analysis	Collection Time-point	
Hematology (CBC)	4 mL blood	Hemoglobin, RBC, MCV, hematocrit, WBC count with differential, and platelet count	Screening Visit 1, Weeks 2-Visit 778	
Biochemistry	8.5 mL blood	Sodium, potassium, chloride, BUN/Urea, *Creatinine, glucose, calcium, phosphorous, total protein, albumin, total bilirubin, AST, ALT, GGT, Alkaline phosphatase, LDH, CK,CRP, Uric acid, (total bilirubin > 1.5 times ULN will be reported as direct and indirect bilirubin),	Screening Visit 1, Weeks 2-Visit 778, *creatinine will be measured once weekly for 3 weeks following randomization	
Iron metabolism	8.5 mL blood	Serum ferritin	Screening V1, V2, Weeks 2-Visit 778	
Viral Serology	Same sample as for chemistry	Hepatitis B: HBsAg and anti-HBs Hepatitis C: Anti-HCV, HCV RNA quantification	Screening Visit 1	
Serum Pregnancy Test	Same sample as for chemistry	Serum β-HCG for women of child-bearing potential	r women of child-bearing Screening Visit 1	
Urine Pregnancy Test	> 1 mL urine in clean container	Urine HCG for women of child-bearing potential	Visit 777	
Urinalysis	30 mL (midstream urine sample)	Specific gravity, pH, semi-quantitative "dipstick" evaluation of glucose, protein, bilirubin, ketones, leukocytes, blood.	Screening Visit 1 and Weeks 2-Visit 778	

Evaluation	Sample collection	Analysis	Collection Time-point
Urinary protein / creatinine ratio	10 mL urine (non-first void morning specimen)	Total protein and creatinine	Screening Visits 1 and 2, Weeks 2- Visit 778.
Oral Glucose Tolerance Testing *	2 mL blood, two times	Blood glucose test	Screening Visit 1, then every year
Brain Natriuretic Peptide (BNP)	2 mL blood	BNP	Randomization, then unscheduled visits if CHF is suspected

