#### Proportion of patients with worsening of glucose metabolism

An annual oral glucose tolerance test will be carried out to evaluate changes of glucose metabolism compared to the baseline status. The proportion of patients with an increase in glucose metabolism category (normal, impaired glucose metabolism, diabetes mellitus) based on the American Diabetes Association criteria (American Diabetes Association 2009) compared to their baseline result will be determined at each timepoint, i.e. 1, 2, years after randomization. For this classification, fasting and 2-hour post-prandial plasma glucose levels will be measured.

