#### Criteria for impaired glucose metabolism:

• fasting plasma glucose (FPG) levels ≥ 100 mg/dl (5.6 mmol/L) but <126 mg/dl (7.0 mmol/L)

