#### OR

- FPG ≥ 126 mg/dl (7.0 mmol/L). Fasting is defined as no caloric intake for at least 8 hours. **OR**
- 2 hour postload glucose ≥ 200 mg/dl (11.1 mmol/L) during an OGTT. The test should be performed as described by WHO, using a glucose load containing the equivalent of 75 g anhydrous glucose dissolved in water.

Frequency and shift tables will be provided for each treatment group. Results will also be shown separately for each year since randomization.

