2.7.1.3 Proportion of patients with worsening of glucose metabolism

An annual oral glucose tolerance test will be carried out to evaluate changes of glucose metabolism compared to the baseline status. The proportion of patients with an increase in glucose metabolism category (normal, impaired glucose metabolism, diabetes mellitus) based on the American Diabetes Association criteria (American Diabetes Association 2009) compared to their baseline result will be determined at each time point, i.e. 1, 2, ..., years

RAP M3 Amendment 4

after randomization. For this classification, fasting and 2-hour post-prandial plasma glucose levels will be measured.

Criteria for impaired glucose metabolism:

fasting plasma glucose (FPG) levels $\geq 100 \text{ mg/dL}$ (5.6 mmol/L) but $\leq 126 \text{ mg/dL}$ (7.0 mmol/L)

OR

2-h values in the oral glucose tolerance test (OGTT) of \geq 140 mg/dL (7.8 mmol/L) but <200 mg/dl (11.1 mmol/L)

Criteria for diabetes mellitus:

• non-fasting plasma glucose $\geq 200 \text{ mg/dL } (11.1 \text{ mmol/L})$

OR

FPG > 126 mg/dL (7.0 mmol/L). Fasting plasma glucose is defined as no caloric intake for at least 8 hours

OR

2 hour post load glucose \geq 200 mg/dL (11.1 mmol/L) during an OGTT. As described by WHO, the test use a glucose load containing the equivalent of 75 g anhydrous glucose dissolved in water

Frequency and shift tables will be provided for each treatment group. Results will also be shown separately for each year since randomization.

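### The glucose tolerance test may be drawn after a 5-hour fast, the endpoint defines fasting as 8 hours, and no rule covers the samples in between

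*Protocol*

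**What the plan says.** **Collection.** Protocol Table 7-1, footnote 17, schedules the oral glucose tolerance test at screening, annually and at treatment discontinuation, with the instruction "Patients should fast for at least 5 hours prior to the test being drawn". The footnote to Table 7-2 repeats it. Table 7-2 lists two draws per test ("2 mL blood, two times").

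**Endpoint.** Protocol section 3.2.1 names as a secondary efficacy endpoint the "Proportion of patients with a worsening of glucose metabolism from baseline as assessed by annual oral glucose tolerance test (OGTT"). Section 10.5.1.1 adds: "For this classification, fasting and 2-hour post-prandial plasma glucose levels will be measured".

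**Classification.** Impaired glucose metabolism is "fasting plasma glucose (FPG) levels ≥ 100 mg/dl (5.6 mmol/L) but <126 mg/dl (7.0 mmol/L") or a 2-hour value in the impaired range, which starts at 140 mg/dL. Diabetes is "FPG ≥ 126 mg/dl (7.0 mmol/L"), or a 2-hour value of at least 200 mg/dL, or a separate criterion at 200 mg/dL that does not depend on fasting. The protocol states that last criterion for a casual sample with symptoms. The SAP states it for a non-fasting sample and does not mention symptoms.

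**Definition of fasting.** Under the FPG criterion for diabetes the protocol says "Fasting is defined as no caloric intake for at least 8 hours". SAP section 2.7.1.3 attaches the definition to the measurement itself: "Fasting plasma glucose is defined as no caloric intake for at least 8 hours".

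**The concern.** The collection rule and the classification rule for the same sample have different minimum fasts. A site that follows the visit schedule exactly can produce a first-draw value that the endpoint's definition does not recognise as fasting. The plan does not say what happens to that value. It mentions neither recording the length of the fast nor setting a short-fast value aside, and SAP section 4, which lists changes to the protocol-specified analyses, does not address the difference.

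At stake is the reproducibility of a named secondary endpoint. Two programmers working in good faith from the same data could build different shift tables: one would apply the FPG limits to every first draw, the other only to draws that meet the 8-hour definition. Part of the movement between categories would then reflect how long a patient had fasted.

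**Working it through.** No sample size, power or event count is involved, and the plan states no figure to reproduce. The check sets the passages side by side and follows a sample through them.

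| Place | Minimum fast | Applies to |
|---|---|---|
| Protocol Table 7-1, footnote 17 | 5 hours | drawing the test |
| Protocol Table 7-2, footnote | 5 hours | drawing the test |
| Protocol 10.5.1.1, diabetes criterion | 8 hours | FPG limit of 126 mg/dL |
| Protocol 10.5.1.1, impaired criterion | none stated | FPG range from 100 mg/dL |
| SAP 2.7.1.3 | 8 hours | FPG as such, so reasonably both limits |

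**Step 1: which samples are affected.** The gap is 8 − 5 = 3 hours. A fast of 8 hours or more satisfies every row. A fast under 5 hours breaks the visit schedule. Only a fast of 5 to under 8 hours satisfies the schedule and fails the definition.

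**Step 2: what the missing rule does to one patient.** The values here are hypothetical. Take a 6-hour fast, a first draw of 130 mg/dL and a 2-hour value of 130 mg/dL.
- If the first draw is treated as FPG, 130 exceeds 126 and the patient is classed as diabetic.
- If the SAP's 8-hour definition is applied literally, the first draw is not FPG. It is below the non-fasting limit of 200 mg/dL, and the 2-hour value is below 140 mg/dL. No criterion is met and the patient is normal.

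With a first draw of 110 mg/dL instead, the two readings give impaired and normal. Because the criteria are joined by OR, a normal 2-hour value does not override the first draw.

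**Step 3: what this does to worsening.** The endpoint compares each annual category with the patient's own baseline, and the same instruction applies at screening. Assume that a short fast leaves some residual meal effect, which the documents do not quantify.
- A raised baseline category can hide a later true worsening.
- A raised follow-up category can create a worsening that did not occur.

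The two errors work in opposite directions, so the net direction is not fixed.

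**Step 4: weight of one patient.** With 210 patients at 2:1, the arms have 210 × 2/3 = 140 and 210 × 1/3 = 70 patients. If all are evaluable, one misclassified patient moves the proportion by 1/140 = 0.7 percentage points on deferasirox or 1/70 = 1.4 percentage points on placebo.

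**Step 5: how many patients.** This cannot be computed. The documents give neither the distribution of fasting times nor any glucose values.

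**The case against.** The strongest reply has four parts.

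- **Five hours is a floor.** A reader might infer that samples are taken at 5 hours. The text does not support that. Patients who fast 8 hours or more meet every passage, and nothing shows how many fall below. This stands.
- **The SAP may already exclude short-fast samples.** A reader might infer that the plan misclassifies these patients. Read literally, the SAP says that a sample under 8 hours is not FPG, so the 100 and 126 mg/dL limits would not reach it, and a separate non-fasting criterion exists. The protocol, moreover, ties the 8 hours only to the diabetes criterion. This also stands, and it limits the point: the defect is an unresolved conflict without an explicit rule, not a demonstrated wrong classification. It does not remove the point, because the literal reading is not stated as a rule, and the plan does not say that fasting length, which would be needed to apply it, is recorded.
- **Little depends on it.** Both arms are blinded and follow one instruction, so the error should be mostly non-differential. The endpoint is reported as frequency and shift tables, SAP section 2.7.2 says no hypothesis is tested for secondary endpoints, and the primary endpoint is untouched. This stands and sets the priority.
- **It is late.** Amendment 4 dates study initiation to November 2009. Recruitment was planned until December 2014 with three further years, and the current SAP is dated 19 April 2018. A changed footnote will reach few tests, if any. That argues for handling the matter mainly in the analysis.

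**Conclusion.** The inconsistency is real and lies in current text of both documents. A sample drawn after 5 to under 8 hours complies with the visit schedule, is not FPG by the endpoint's definition, and has no stated classification, although it can by itself change a patient's category.

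The size is unknown. A reader might be tempted to assume a glucose distribution and a residual meal effect and quote an inflated share above 100 or 126 mg/dL. The documents supply neither input. Such a figure would also apply the shift to every patient, describe one visit instead of change from baseline, and ignore patients already classified by the 2-hour value. Nor do the documents support a claim of bias between the arms: added noise that may blur a difference is the more plausible consequence.

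The conclusion assumes that at least some patients fasted for under 8 hours, and that the SAP's definition of FPG is meant to govern both limits. The effect is confined to one descriptive secondary endpoint. It is worth correcting because the correction is cheap, but it does not threaten the trial's main result.

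**What to change.** 1. **Protocol.** Reconcile footnote 17 of Table 7-1 and the footnote of Table 7-2 with the 8-hour definition that the endpoint uses, for any tests still to be done. The cost is a wording change.
2. **SAP section 2.7.1.3, before unblinding.** State how a first-draw value is classified when the fast was under 8 hours or its length is unknown, and apply the same rule at baseline and follow-up. The rule must cover unknown length. If it admitted only documented 8-hour fasts and the duration was not captured, it could discard most or all FPG values and leave baseline and follow-up classified on different criteria.
3. **Sensitivity table.** Repeat the frequency and shift tables with baseline and follow-up classified on the 2-hour value only. Two draws per test are already planned, so no new data are needed, and the cost is one extra table.

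One limit remains. The 2-hour value comes from the same test under the same 5-hour instruction, so the table in item 3 is a check on the result, not a full correction.

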# 7.1 Information to be collected on screening failures

A screening log of all patients screened for this study, at each study center, will be kept. This log will include patient number, demographic details, and reason why the patient was a screen failure. Sites should also maintain pre-screening logs capturing all of the reasons why a patient was not eligible for screening. The following information of patients who are screened but fail to be randomized will be collected in the eCRF: demographics, screening log and serious adverse events.

Should a patient screen fail but subsequently become eligible by newly meeting entry criteria resulting from a change in their parameters or due to a protocol amendment, patients may be re-screened. All screening labs outlined in Screening Visit 1 and Screening Visit 2 must be repeated. All other procedures (ECHO, abdominal ultrasound, bone marrow biopsy or aspiration, ocular and audiometery examinations, etc.) do not need to be repeated if they have been performed within 6 months of the original screening visit date.

# 7.2 Patient demographics/other baseline characteristics

At Visits 1 and/or 2, data will be collected on patient characteristics including demographic information (age, sex, ethnicity, etc.), other background or relevant medical history/current medical condition (6 months) prior to study entry: hemoglobin and transfusion history, disease history, vital signs, previous iron chelation therapies).

Other assessments done for the purpose of determining eligibility for the study include IPSS, history of HIV positive test result (ELISA or Western Blot), active hepatitis B and/or C, urinalysis, ALT/AST, serum creatinine, serum ferritin, serum pregnancy test, other biochemistry studies, echocardiography, bone marrow history/examination.

#### 7.3 Treatments

Information on study drug will be collected on the Dose Administration Record (DAR) eCRF and will include the planned dose (mg/kg/day), actual total daily dose (mg) taken, reason for the dose, start date and end date.

Compliance will be assessed by the investigator and/or study personnel at each visit using tablets/vial counts and information provided by the patient or the caregiver. This information should be captured in the source document at each visit, and also entered on the appropriate eCRF. Concomitant medications/significant non-drug therapies both prior to start of study drug and after start of study drug will be assessed and thus have to be recorded in the eCRF.

Information collected on the Concomitant Medications/Significant Non-drug Therapies eCRF will include concomitant medications/significant non-drug therapy, reason for the medication/therapy, start date, and end date.

The number of tablets of study medication of each strength (125 mg, 250 mg, 500 mg) dispensed will be recorded during the study in the source documents using a drug dispensing log (see [Post-text supplement 2]) and Drug Compliance eCRF. Empty bottles and unused medication will be returned by the patient to the study site. Unused study medication tablets will be counted and recorded by the investigator/pharmacist/study staff involved in the study, according to local legal requirements.

# 7.4 Efficacy

# 7.4.1 Composite primary endpoint

The primary objective is to evaluate deferasirox and placebo with regard to event-free survival (including death and non-fatal events related to cardiac and liver function and transformation to AML). The EAC will evaluate the criteria for the composite primary efficacy endpoint on an ongoing basis.

The composite primary endpoint (event-free survival) consists of both death and non-fatal events. Non-fatal events include worsening cardiac function based on echocardiographic evidence, hospitalization for congestive heart failure, liver function impairment reflected by elevated ALT or AST and bilirubin values, confirmed liver cirrhosis, and transformation to AML. Details regarding the components of the composite endpoint are described in Section 7.5.7, Section 7.5.10 and Section 7.5.11.

# 7.5 Safety

Safety assessments will consist of monitoring and recording all AEs and SAEs, laboratory safety assessments (hematology, blood chemistry and urinalysis) and clinical evaluations (physical examinations, vitals signs, body weight, auditory and ocular tests, ECG) as outlined in Table 7-1.

## 7.5.1 Adverse events

An adverse event for the purposes of this protocol is the appearance of (or worsening of any pre-existing) undesirable sign(s), symptom(s), or medical condition(s) occurring after signing the informed consent even if the event is not considered to be related to the study drug(s). However, it must be noted that MDS is not considered an adverse event. MDS is a required condition for study entry and is expected to be reported as Medical History for all patients. Time to disease progression is a secondary efficacy endpoint. Please refer to Section 6.1 for the protocol-specific definitions of study drug and study treatment.

Adverse events (but not serious adverse events) occurring before starting study treatment but after signing the informed consent form are recorded on the Medical History/Current Medical Conditions eCRF. Abnormal laboratory values or test results that induce clinical signs or symptoms, are considered clinically significant, require therapy (e.g., any hematological abnormality that requires transfusion or cytokine treatment), or interruption of study medication should be recorded on the Adverse Events eCRF under the signs, symptoms or diagnosis associated with them. Abnormal Laboratory values that do not meet this criteria are not reported as Adverse Events. SAEs occurring after signing the Informed Consent are recorded on the Adverse Event eCRF.

The occurrence of adverse events should be sought by non-directive questioning of the patient at each visit during the study. Adverse events also may be detected when they are volunteered by the patient during or between visits or through physical examination, laboratory test, or other assessments. As far as possible, each adverse event should be evaluated to determine:

- 1. The severity grade (mild, moderate, severe)
- 2. Its relationship to deferasirox (suspected/not suspected)

- 3. Its duration (start and end dates or if continuing at final examination)
- 4. Action taken (no action taken; study drug dosage adjusted/temporarily interrupted; study drug permanently discontinued due to this adverse event; concomitant medication taken; non-drug therapy given; hospitalization/prolonged hospitalization)
- 5. Whether it is serious, where a serious adverse event (SAE) is defined as one which:
  - Is fatal or life-threatening
  - Results in persistent or significant disability/incapacity
  - Constitutes a congenital anomaly/birth defect
  - Requires inpatient hospitalization or prolongation of existing hospitalization, unless hospitalization is for:
    - Routine treatment or monitoring of the studied indication, not associated with any deterioration in condition
    - Elective or pre-planned treatment for a pre-existing condition that is unrelated to the indication under study and has not worsened since signing the informed consent
    - Treatment on an emergency outpatient basis for an event not fulfilling any of the definitions of an SAE given above and not resulting in hospital admission
    - Social reasons and respite care in the absence of any deterioration in the patient's general condition
  - Is medically significant, i.e., defined as an event that jeopardizes the patient or may require medical or surgical intervention to prevent one of the outcomes listed above

